# 9.7. Data Analysis

Detailed methodology for summary and statistical analyses of data collected in this study will be documented in an SAP, which will be dated, filed, and maintained by the sponsor. The SAP may modify the plans outlined in the protocol; any major modifications of outcome definitions or their analyses would be reflected in a protocol amendment.

### 9.7.1. Data Lag

In the analysis of CMS Medicare data, the approach to account for data lags in the RCA and SCRI is to delay the analysis for at least 60 days to allow for at least 90% capture of data for post-vaccination follow-up period. Prior research suggests that ≥90% of IP and OP claims were submitted to the CMS within 2 months after service date. (14, 15) While imposing a lag in the analysis negatively impacts the timeliness of safety assessment, it allows the data to be more complete and thus increases the validity of results. In a non-pandemic setting where the initial uptake for the RSV vaccines is modest, the trade-off between timeliness and validity is deemed acceptable, and a similar approach has been used in prior safety monitoring for Shingrix after the vaccine approval.(27) Data lags will be assessed during the interim reports and a lag longer than 60 days (e.g., 90 days) may be considered for the final analysis, as necessary and feasible, to accrue the most stable data.

The PharMetrics Plus data has a data lag of approximately 6 months due to claims adjudication and completeness, making it unsuitable for the monthly sequential monitoring component (i.e., RCA) of the study. However, it will effectively contribute to the descriptive analysis (SCRI may be considered contingent on sufficient sample size), to be conducted towards the end of each RSV season and at the final two-season pooled analysis. This

analytic arrangement accounts for the data lag and still generates timely safety data for GBS in individuals aged 60-64 years following exposure to ABRYSVO.

# 9.7.2. Description of ABRYSVO Recipients

Covariates will be assessed among the study population aimed for SCRI analysis, RCA analysis and the descriptive analysis for individuals aged 60-64 (Section 9.1.4). Patient demographic and clinical characteristics including age on index, gender, race, geographic region, concurrent immunizations, prior infections, and selected comorbidities will be reported. Demographic variables will be assessed on the index date or during the baseline period, as described in Section 9.3.3. If multiple records exist, the record closest to the index date will be used.

Continuous variables will be summarized using mean  $\pm$  SD, median, and interquartile range. Categorical variables will be summarized using counts and proportions. 95% CIs will be provided where applicable.

### 9.7.3. The Statistical Analysis for the RCA

In order to conduct near real-time surveillance to monitor the risk of GBS following RSV vaccination, a group sequential testing approach will be used to compare the observed rates of GBS following vaccination to an expected incidence rate of GBS (referred to as the background rate; Section 9.7.3.1).(27, 28) Each month, an adjusted RR of GBS will be estimated to conduct an exact sequential Poisson-based likelihood ratio test using unifying family group sequential methods, previously described by Nelson et al. (27, 28) This methodology is suited for continuously accumulating data, enabling timely monitoring and decision-making regarding vaccine safety concerns.

The group sequential testing will be used to conduct sequential tests with cumulative monthly data, with the first monthly analysis starting December 2024 when >90% completeness in follow-up data for ABRYSVO vaccinations through 10 September 2024 are expected. The first RCA look will include cumulative data from the 2023/2024 RSV season and initial uptake data from the 2024/2025 season. A total of 6 monthly RCA looks are planned.

The RR of GBS will be the target parameter, defined as the ratio of the observed GBS rate and the expected GBS rate in the ABRYSVO population. We will conduct one-sided tests where the null hypothesis is that the observed rate of GBS in the ABRYSVO cohort is no greater than 2 times the comparator rate. The alternative hypothesis is that the observed rate in the ABRYSVO cohort is greater than 2 times than the comparator rate:

 $H_0$ : RR  $\leq 2$ 

 $H_a$ : RR >2

In previous literature, a pre-specified the test margin with an overall alpha of 1% was used to obtain a null hypothesis of "RR  $\leq$ 2.5" for assessing the risk of GBS following COVID-19 vaccination to avoid minimal risk increases that were unlikely to be clinically relevant.(29) In this study, the RR and test margin are more conservative to declare a safety signal.

The expected number of events under the null hypothesis will be used as the upper limit on number of tests to be conducted (i.e., the pre-specified surveillance length). Sequential testing will continue until a signal is observed (or the pre-specified surveillance length is reached), after which formal sequential analyses will be stopped and descriptive statistics will be monitored going forward until the end of the surveillance to increase the precision estimates for the incidence of GBS.

The RCA is meant to rapidly detect if there is a signal for an elevated risk of GBS following vaccination with ABRYSVO. In the monthly analyses, if the risk meets the signal threshold, rejecting the null does not imply a causal association and further steps will be taken to evaluate the robustness of signal and to characterize the signal, including:

- 1. Post-signal data quality assurance, including checking for possible duplications of vaccinations, GBS events or individuals; coding issues such as unexpected codes for vaccinations; and changes in claims recording processes.
- 2. A signal characterization will be performed to assess potential confouding factors, which will include a description of demographics, clinical characteristics, and GBS risk factors among the individuals who received ABRYSVO and had a GBS event.

Based on the post-signal data quality assurance check and the signal characterization, the RCA may be re-run to see if the positive signal persists when any potentially invalid GBS cases are excluded.

Lastly, an SCRI analysis will be conducted to further evaluate signals from the RCA results.

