#### 9.3.2. Outcomes

The outcome of interest is GBS diagnosis, which will be identified from IP and OP claims using ICD-10-CM code G 61.0.

An incident GBS case will be defined as the first occurrence of a primary discharge diagnosis of GBS in the IP setting post-vaccination. The date of the case's onset will be defined as the date of hospitalization unless there is a claim with a GBS diagnosis in another medical setting (e.g., OP) in the prior 7 days. In that case, the earlier claim, irrespective of healthcare setting, will represent the date of onset. This claims-based algorithm in Medicare data has a PPV of 71.2% – 78.6% when validated against medical records using the Brighton criteria and has been used to reliably identify GBS cases among Medicare beneficiaries.(9, 22, 23) In a recent FDA analysis evaluating GBS risk following RSV vaccination in the Medicare data, the algorithm for GBS had a PPV of 62.3% in the post-vaccination risk interval of 1-42 days and a PPV of 81.8% in the post-vaccination control interval of 43-90 days, based on chart review.(24)

The risk window of 42 days post-vaccination is generally recommended by the Brighton Collaboration GBS case definition. (19) Within the ABRYSVO clinical and surveillance studies, over 90% of GBS events have been found to occur within 21 days of vaccination.(13) In this study, for the RCA, the primary risk interval is defined as 1—21 days post-vaccination to prioritize timely analysis; a secondary risk interval of 1—42 days post-vaccination will also be analyzed. For the SCRI, the primary post-vaccination risk interval is defined as 1—21 days post-vaccination and the secondary post-vaccination risk interval is defined as 1—42 days post-vaccination. The control interval for the SCRI analysis is defined as 43—84 days post-vaccination. For the SCRI analysis, GBS diagnosis will be identified during the risk and the control intervals to compare the risk of GBS occurrence within the two intervals.

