### 9.7.3.1. The Background Rate of GBS

The observed number of GBS cases in the ABRYSVO-vaccinated population will be compared to an expected number of GBS cases based on the background rate of GBS calculated for a historical influenza-vaccinated population from the CMS Medicare database. Although the background rate of GBS has been previously estimated from the general Medicare beneficiaries (25), we hypothesize that the historical influenza-vaccinated comparator group will have greater similarity to recipients of RSV vaccines than the general Medicare beneficiaries in terms of demographics, clinical characteristics and health-seeking behavior. Furthermore, the GBS rates of the historical comparator group will be adjusted for important covariates such as age, gender, and race to align with characteristics of the recipients of RSV vaccines; other variables (e.g., nursing home status) may also be included as feasible. Moreover, Medicare beneficiaries that are not qualified due to age will be excluded to match the inclusion criteria of the ABRYSVO-vaccinated study population.

The background rates of GBS will be estimated for individuals in the CMS Medicare database that received the seasonal influenza vaccines in the 2022 and 2023 influenza seasons (before ABRYSVO approval). This decision was influenced by recent literature indicating a 41.2% increase in the prevalence of GBS in North America between 1990 and 2019 and also an internal preliminary analysis in Optum's de-identified Market Clarity Data indicating a significant increase in annual incidence rates of GBS in older adults over time (Figure 8).(25, 30) This internal analysis was previously presented to the FDA in a document titled "Request for Comments and Advice Regarding RSV Vaccine Safety Study (28 August

2024)." Considering the updated knowledge regarding an increasing trend in incidence of GBS, it is more appropriate to use the more recent historical cohorts for background rate estimation to minimize biases due to secular trends.

15 14 13 12 ncidence rate per 100,000 PY 11 10 9 8 7 3 2 1 0 2017 2018 2019 2020 2021 2022 2023 Year ---- 60+y & 2+ CCI

Figure 8. Incidence rates of GBS among adults 60+ years of age by Charlson Comorbidity (CCI) (0,1 conditions versus 2+ conditions) in the United States from 2017-2023

Abbreviations: CCI, Charlson Comorbidity Index; PY, person-years.

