### 9.7.6.2. Positive Predictive Values (PPV)-Adjusted Quantitative Bias Analysis

A PPV-adjusted analysis will be conducted to assess bias due to outcome misclassification and uncertainty in the claims-identified cases of GBS. Misclassification can occur if cases of GBS are under-identified or if other conditions are mistakenly classified as GBS.

The PPV-adjusted analysis will be performed using quantitative bias analysis (QBA) using PPVs available from prior studies that have conducted medical record review to validated GBS diagnoses following vaccine exposures.(12) The PPV estimate for GBS in CMS Medicare database for individuals aged 65 or older that will be used for adjustment in the study is 71.0% (95% CI: 63.0%, 79.0%).(9) For the SCRI analysis, differential PPV adjustment will also be used based on the FDA's October 2024 ACIP presentation, which reported different PPVs for GBS diagnosis in the risk and control intervals: 62.3% (48.8 - 74.1%) for claims-identified GBS cases during the 1-42 day risk interval and 81.8% (61.5 - 92.7%) during the 43-90 day control interval.(24) The study will integrate updated information on PPVs as they become available in the published literature or regulatory studies for the duration of the study.

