# 9.7.6.3. The PPV-adjusted sensitivity analysis will also be conducted in the RCA. Seasonality and PPV-Adjusted Analysis

A seasonality and PPV-adjusted analysis may also be considered, as feasible, to account for both potential confounders that could bias outcome rate estimates.

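### The post-signal RCA re-run may drop doubtful GBS cases among ABRYSVO recipients, but nothing requires the same exclusion in the historical influenza cohort behind the expected count

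*Protocol*

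**What the plan says.** Section 9.7.3 tests an observed rate against an expected one: "the null hypothesis is that the observed rate of GBS in the ABRYSVO cohort is no greater than 2 times the comparator rate". Formal sequential testing stops once a signal occurs. Two steps then follow:

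- Data quality assurance, which includes "checking for possible duplications of vaccinations, GBS events or individuals", unexpected codes and changes in claims recording.
- A signal characterization, describing demographics, clinical characteristics and "GBS risk factors among the individuals who received ABRYSVO and had a GBS event".

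On the basis of both, "the RCA may be re-run to see if the positive signal persists when any potentially invalid GBS cases are excluded". The section does not define an invalid case. It closes by saying that an SCRI analysis will evaluate RCA signals further.

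Section 9.7.3.1 describes the other side of the ratio, an "expected number of GBS cases based on the background rate of GBS calculated for a historical influenza-vaccinated population". Its adjustments concern age, gender, race and possibly nursing home status. It also restricts the cohort to people who qualified for Medicare by age. It mentions no review or removal of cases.

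On false positives, Section 9.3.2 reports that "the algorithm for GBS had a PPV of 62.3% in the post-vaccination risk interval of 1-42 days", and Section 9.7.6.2 gives the PPV estimate "that will be used for adjustment in the study is 71.0"% (95% CI 63.0% to 79.0%). Section 9.7.6.3 adds: "The PPV-adjusted sensitivity analysis will also be conducted in the RCA". It does not say whether the adjustment covers the observed count, the expected count or both.

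**The concern.** By the protocol's own PPVs, GBS identified from claims includes false positives, and the historical influenza cohort comes from the same Medicare claims. The ratio is fair only while both counts are handled alike. Removing doubtful cases from the observed count alone compares a cleaned numerator with an uncleaned expectation.

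The exclusion is also chosen after the result is known, only when a signal has occurred, and without a stated definition. Because it may rest on clinical features and risk factors, it is not confined to duplicates or miscoding. The bias always runs downward, towards dismissing a safety signal.

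The timing matters. The RCA report is due on 08 August 2025. The 2024/2025 and pooled SCRI results come in the final report on 30 January 2026, and Section 9.5 expects the pooled SCRI to have 80% power only for a 3- to 4-fold risk. A statement that the signal did not persist could stand for months.

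**Working it through.** **Plan's own figure.** The protocol gives no figure for the re-run, so the calculated design figure available is SCRI Table 1. For IRR 5.0 with equal intervals, two-sided 0.05 and 80% power, the self-controlled case series sample-size formula gives 14.86, rounded up to the stated 15 events. The 21-day N is 3 / 0.0000026 = 1,153,846, as stated. The per-person risk behind it is 0.000046 × 21/365 = 0.00000265. The same rate is used below.

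**Inputs.**
- Doses: 2,000,000 (Section 9.5, pooled SCRI figure). RCA indexing ends earlier, so 1,000,000 is shown too.
- Background rate: 4.6 per 100,000 person-years (Section 9.5), standing in for the influenza-cohort rate, which is not given.
- Null margin: RR ≤ 2, one-sided (Section 9.7.3).
- Alpha: not stated for the RCA. Assumed 5%, with 1% as an alternative.
- Looks: six are planned, but no boundary is given, so a single exact Poisson look is used.
- Fraction of cases kept, k: hypothetical. 0.71 and 0.623 are borrowed from the stated PPVs; 0.90 represents light pruning.

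**Effect on the RR.** RR = O/E.
- Observed-only exclusion: kO/E = k × RR.
- Symmetric exclusion: kO/kE = RR.

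A claims-based RR of 4 becomes 4 × 0.71 = 2.84 or 4 × 0.623 = 2.49 under observed-only exclusion. It stays at 4 under symmetric exclusion. For the observed-only point estimate to remain above 2, the starting RR must exceed 2/0.71 = 2.82 or 2/0.623 = 3.21.

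**Effect on the test.** E = 2,000,000 × 0.000046 × 21/365 = 5.29, so the null mean is 2 × 5.29 = 10.59. At alpha 5% the critical count is 17, since P(X ≥ 17) = 0.042 and P(X ≥ 16) = 0.072.
- Observed-only: the count has mean 4 × 5.29 × k and must still reach 17. At k = 0.71 the mean is 15.03.
- Symmetric: the null mean is also multiplied by k. At k = 0.71 it is 7.52 (critical count 13); at k = 0.623 it is 6.60 (critical count 12).

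Probability that the re-run meets its threshold when the true RR is 4, as observed-only / symmetric:

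| Setting | E | Critical count, no exclusion | No exclusion | k = 0.90 | k = 0.71 | k = 0.623 |
|---|---|---|---|---|---|---|
| 2 million, 21 days, 5% | 5.29 | 17 | 0.846 | 0.712 / 0.789 | 0.339 / 0.735 | 0.179 / 0.666 |
| 2 million, 21 days, 1% | 5.29 | 20 | 0.630 | 0.444 / 0.626 | 0.127 / 0.435 | 0.048 / 0.448 |
| 1 million, 21 days, 5% | 2.65 | 10 | 0.613 | 0.482 / 0.482 | 0.225 / 0.478 | 0.131 / 0.341 |
| 2 million, 42 days, 5% | 10.59 | 30 | 0.980 | 0.923 / 0.975 | 0.529 / 0.921 | 0.265 / 0.915 |

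These probabilities are not conditional on a first signal. In the first row, a pruned count of 17 implies a raw count of at least 17. Given a first signal, observed-only persistence is therefore 0.339/0.846 = 0.40 at k = 0.71 and 0.179/0.846 = 0.21 at k = 0.623. The counts are small whole numbers, so light pruning can leave the two approaches equal, as in the third row at k = 0.90.

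**PPV adjustment.** If the observed side had PPV 62.3% and the historical side 71.0%, correcting both would multiply the RR by 0.623/0.710 = 0.88. Correcting the observed side alone would multiply it by 0.62.

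**The case against.** A reader might infer that the plan prescribes observed-only exclusion and so lets a true signal be erased by construction. The documents do not support that. Section 9.7.3 never says the expected count is held fixed; it is silent. The signal is declared before any re-run, the re-run is optional and serves as a robustness check, and the SCRI follows whatever it shows. A footnote to Section 9.1.1 adds that the RCA will not be used to determine association.

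The size of the exclusion is also open. Section 11 says that individual data are neither retrieved nor validated, so no chart review will remove a share equal to one minus the PPV. The named quality checks are mostly record errors, which may properly be removed. Losing a signal that only just reached the boundary would prove little: dropping one of 17 cases gives p = 0.072. Symmetric exclusion loses it too, with 12 cases against a null mean of 7.52 (p = 0.080) or 11 against 6.60 (p = 0.072).

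On PPV, nothing says that only the observed side will be adjusted. The 62.3% figure is offered for the SCRI and for days 1-42. A single PPV applied to both sides would cancel. Finally, the protocol leaves sensitivity-analysis detail to the SAP, which is not at hand.

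All of this limits the point, but a defect remains. The protocol itself sets an exclusion triggered by the signal, and names ABRYSVO cases alone as those to be characterized. Without chart review, doubtful validity can only be a judgement from claims, and the same judgement can be made on the historical claims.

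**Conclusion.** The point holds as a gap that permits a biased robustness check. It does not show that a signal would be cancelled. If exclusions go beyond record errors and are made on the observed side only, the re-run RR falls by the fraction removed.

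At 2 million doses, 21 days, alpha 5% and a true RR of 4, the chance of meeting the threshold falls from 85% with no exclusion to 34% (29% removed) or 18% (38% removed). Symmetric exclusion gives 74% or 67%, and that loss is one of precision, not bias. At alpha 1% the figures are 63% with none, 13% or 5% observed-only, and 44% or 45% symmetric.

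The direction needs none of these numbers. The size rests on the assumed alpha, a single look, the planning rate, equal retained fractions on both sides, and removal shares that are hypothetical. The PPV limb is conditional: Section 9.7.6.3 should say which counts are adjusted.

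**What to change.** In Section 9.7.3:

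1. State that post-signal exclusions other than record errors (duplicates, wrong codes) must follow a claims-based rule, applied identically to the historical influenza cohort, with the expected count recomputed.
2. Run the record-error checks, such as de-duplication, on that cohort as well.
3. Report the original result beside the re-run, and say that the original result remains the signal decision.

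In Sections 9.7.6.2 and 9.7.6.3, state that the RCA adjustment applies PPV to both counts: adjusted RR = RR × PPV(observed) / PPV(historical).

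The cost is a few sentences in the protocol or SAP and one extra run of the same program on the historical cohort. Precision in the re-run will be slightly lower.

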### 9.7.3.1. The Background Rate of GBS

The observed number of GBS cases in the ABRYSVO-vaccinated population will be compared to an expected number of GBS cases based on the background rate of GBS calculated for a historical influenza-vaccinated population from the CMS Medicare database. Although the background rate of GBS has been previously estimated from the general Medicare beneficiaries (25), we hypothesize that the historical influenza-vaccinated comparator group will have greater similarity to recipients of RSV vaccines than the general Medicare beneficiaries in terms of demographics, clinical characteristics and health-seeking behavior. Furthermore, the GBS rates of the historical comparator group will be adjusted for important covariates such as age, gender, and race to align with characteristics of the recipients of RSV vaccines; other variables (e.g., nursing home status) may also be included as feasible. Moreover, Medicare beneficiaries that are not qualified due to age will be excluded to match the inclusion criteria of the ABRYSVO-vaccinated study population.

The background rates of GBS will be estimated for individuals in the CMS Medicare database that received the seasonal influenza vaccines in the 2022 and 2023 influenza seasons (before ABRYSVO approval). This decision was influenced by recent literature indicating a 41.2% increase in the prevalence of GBS in North America between 1990 and 2019 and also an internal preliminary analysis in Optum's de-identified Market Clarity Data indicating a significant increase in annual incidence rates of GBS in older adults over time (Figure 8).(25, 30) This internal analysis was previously presented to the FDA in a document titled "Request for Comments and Advice Regarding RSV Vaccine Safety Study (28 August

2024)." Considering the updated knowledge regarding an increasing trend in incidence of GBS, it is more appropriate to use the more recent historical cohorts for background rate estimation to minimize biases due to secular trends.

15 14 13 12 ncidence rate per 100,000 PY 11 10 9 8 7 3 2 1 0 2017 2018 2019 2020 2021 2022 2023 Year ---- 60+y & 2+ CCI

Figure 8. Incidence rates of GBS among adults 60+ years of age by Charlson Comorbidity (CCI) (0,1 conditions versus 2+ conditions) in the United States from 2017-2023

Abbreviations: CCI, Charlson Comorbidity Index; PY, person-years.

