### 7. RATIONALE AND BACKGROUND

Respiratory syncytial virus (RSV) is a common, contagious virus that causes mild, cold-like symptoms, but may cause severe disease with a need for hospitalization in infants and older adults.(1) RSV infection in older adults can result in Lower Respiratory Tract Disease (LRTD), which can lead to serious, life-threatening pneumonia and bronchiolitis. According to the Centers for Disease Control and Prevention (CDC), RSV infection causes approximately 60,000 - 120,000 hospitalizations and 6,000 - 10,000 deaths annually among adults ages 65 years of age and older.(1) The U.S. FDA approved RSVpreF (ABRYSVO) RSV vaccine on 31 May 2023 for individuals 60 years of age and older to prevent severe RSV and on 21 August 2023 for pregnant individuals at 32 through 36 weeks gestational age to protect newborns through passive immunity. (2, 3) On 22 October 2024, the vaccine was approved for individuals 18 through 59 years of age who are at increased risk for LRTD.(4) The CDC initially recommended that adults aged 60 years and older receive RSV vaccination using shared clinical decision-making.(5) Following the Advisory Committee on Immunization Practices (ACIP) meeting, the CDC further recommended on 26 June 2024 that all adults aged 75 years and older, and adults aged 60-74 years who are at increased risk for severe RSV disease, should receive the vaccine. (6, 7)

GBS is a rare, serious acute demyelinating disease, where damage to the nerve causes muscle weakness and sometimes paralysis.(8) Although the cause of GBS is not fully understood, the syndrome often follows infection with a virus or bacteria; furthermore, it has been found that there is an increased risk for GBS following vaccine administration, an association that was first observed after the 1976 swine flu vaccinations.(8, 9) GBS is a rare, serious acute demyelinating disease, where damage to the nerve causes muscle weakness and sometimes paralysis.(8) Although the cause of GBS is not fully understood, the syndrome often follows infection with a virus or bacteria; furthermore, it has been found that there is an increased risk for GBS following vaccine administration, an association that was first observed after the 1976 swine flu vaccinations.(8, 9)

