### **Clinical characteristics:**

- History of anaphylaxis
- Previous anaphylaxis of vaccine component
- Hospitalizations in the baseline period and during the follow-up period
- Admission into nursing home/Skilled Nursing Facility (SNF) in the baseline period and during the follow-up period
- Infections in the baseline period and during the follow-up period
  - O Upper or lower respiratory tract infections (including diphtheria, whooping cough, streptococcal sore throat and scarlet fever, varicella with pneumonia, RSV, COVID-19, acute sinusitis, acute tonsilitis, acute bronchitis, influenza, etc.)
  - o Gastrointestinal infections (including cholera, typhoid and paratyphoid fevers, shigellosis, amebic nondysenteric colitis, etc.)
  - Unspecified viral infection
  - o Diarrhea
  - o Fever
  - Campylobacter enteritis
  - o Cytomegalovirus (CMV)
  - o Epstein-Barr Virus (EBV)
  - Hepatitis E Virus (HEV)
  - Zika virus
- Frailty index
- Charlson Comorbidity Index (CCI)
- Smoking status
- Body Mass Index (BMI)
- Immunocompromised status
- Selected comorbidities
  - o Asthma
  - Blood disorders
  - o Chronic lung disease

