### 9.9.2. RCA

• The signal detection of the observed rate of GBS in ABRYSVO recipients in comparison to the estimated background may be subject to residual confounding, although matching on key demographic characteristics will be conducted to increase comparability. Any signals from the RCA will need to be further evaluated in the SCRI analysis.

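### Section 9.7.3.1 names and requires no comorbidity adjuster for the RCA expected count, so the RR may be biased, plausibly but not demonstrably upward

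*Protocol*

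**What the plan says.** Protocol section 9.7.3.1 builds the expected count from people vaccinated against influenza in the 2022 and 2023 seasons. It states that "the GBS rates of the historical comparator group will be adjusted for important covariates such as age, gender, and race" and adds that "other variables (e.g., nursing home status) may also be included as feasible". Nursing home status is the only example of an extra variable. Clinical similarity of the two groups is put forward as a hypothesis: "we hypothesize that the historical influenza-vaccinated comparator group will have greater similarity to recipients of RSV vaccines than the general Medicare beneficiaries".

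Figure 8 in the same section is titled "Incidence rates of GBS among adults 60+ years of age by Charlson Comorbidity (CCI) (0,1 conditions versus 2+ conditions"). It is used there to justify recent calendar years, not to choose adjusters.

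Section 7 gives two successive recommendations. First: "The CDC initially recommended that adults aged 60 years and older receive RSV vaccination using shared clinical decision-making". From 26 June 2024 all adults aged 75 and over are covered, and "adults aged 60-74 years who are at increased risk for severe RSV disease, should receive the vaccine".

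Section 9.3.3 lists CCI, a frailty index and selected comorbidities among the patient characteristics to be captured. Section 9.9.2 says that the RCA comparison "may be subject to residual confounding, although matching on key demographic characteristics will be conducted to increase comparability".

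**The concern.** The recommendation in force during 2024/2025 selects on health within ages 60-74. In the Medicare cohort that means ages 65-74. If uptake followed it, ABRYSVO recipients in that band carry more comorbidity than influenza vaccinees of the same age, gender and race, and standardising on those three variables leaves the difference in place. If GBS is also more frequent with comorbidity, which is the split that the sponsor chose to plot, the expected count is too low and the RR too high.

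At stake are the RR reported from the RCA and the error rate of a test whose null is RR ≤ 2. Formal sequential testing stops once a signal is declared (section 9.7.3). According to the amendment log, version 2.0 updated the recommendation in section 7 and also revised section 9.7.3.1, but the named adjusters still include no comorbidity measure.

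**Working it through.** **Plan's own figure.** The protocol gives no RCA expected count, power or alpha. The only stated figure built on a background rate is Table 1 (4.6 per 100,000 person-years, section 9.5). For IRR 5.0 it has 3 control events:

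- 21 days: 3 / (4.6e-5 × 21/365) = 1,133,540, against 1,153,846 stated. The stated value is exact if the 21-day risk is rounded to 2.6 per million.
- 42 days: 3 / (4.6e-5 × 42/365) = 566,770, against 566,038 stated.

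The rate is therefore a usable input. With about 2 million exposures (section 9.5), the 21-day expected count is 4.6e-5 × 21/365 × 2,000,000 = 5.29. The RCA stops indexing on 10 January 2025, so the real figure is slightly lower.

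**Bias factor.** Let k be the GBS rate ratio for CCI 2+ versus 0-1, pA the share with CCI 2+ among ABRYSVO recipients, and pF the share among the influenza comparator. Then

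B = [1 + pA(k − 1)] / [1 + pF(k − 1)],

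and the reported RR is the true RR × B. The documents give none of k, pA and pF, because the Figure 8 values cannot be read in the text at hand and neither cohort's CCI mix is stated. All are assumptions, with pF = 40% throughout.

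**Share of doses reached by the recommendation.** Similar uptake in the two seasons (section 9.5) puts about half of doses in 2024/2025. Assume half of those are at ages 65-74: 0.5 × 0.5 = 25%. If that quarter moves from 40% to 60% CCI 2+, pA = 0.75 × 40% + 0.25 × 60% = 45%.

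| Scenario | pA | B at k = 2 | B at k = 3 |
|---|---|---|---|
| Only 2024/2025, ages 65-74, shifts | 45% | 1.45/1.40 = 1.036 | 1.90/1.80 = 1.056 |
| Whole cohort shifts | 60% | 1.60/1.40 = 1.143 | 2.20/1.80 = 1.222 |
| Recipients less comorbid | 30% | 1.30/1.40 = 0.929 | 1.60/1.80 = 0.889 |

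A true RR of 1.8 would read 1.8 × 1.036 = 1.86 (k = 2) or 1.8 × 1.056 = 1.90 (k = 3) in the first scenario. At k = 2 in the second it would read 1.8 × 1.143 = 2.06. In the third scenario the expected count is overstated by 1/0.929 − 1 = 7.7% (k = 2) or 1/0.889 − 1 = 12.5% (k = 3).

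**Effect on error.** As a simplification, take one look at 2 million doses and an exact one-sided Poisson test against 2 × 5.29 = 10.59. The planned six-look boundary is not given. Alpha is not stated for this study, so 1% and 5% are both shown. The rule signals at 20 or more cases (1%) or 17 or more (5%). At true RR = 2 the observed count has mean 10.59 × B:

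| B | P(signal), nominal 1% | P(signal), nominal 5% |
|---|---|---|
| 1.000 | 0.6% | 4.2% |
| 1.036 | 0.9% | 5.5% |
| 1.056 | 1.1% | 6.3% |
| 1.143 | 2.3% | 10.7% |
| 1.222 | 4.1% | 16.0% |

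At true RR = 1 the probability of a signal is at or below 0.2% in every scenario run, including k = 4 with pA = 70% (B = 1.41).

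**The case against.** Much of the opposing case stands.

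- **The list is open.** A reader might infer that adjustment is confined to age, gender and race. The text does not support that: the three are examples, others may be added, and section 9.3.3 leaves the final covariate list to the SAP, which was not available here. What remains is that comorbidity is neither named nor required, and that section 9.9.2 itself describes the control as demographic.
- **Direction is not shown.** A reader might infer that the expected count is certainly too low. Figure 8 comes from Optum data rather than Medicare, its values are not legible, a recommendation is not uptake, and influenza vaccinees aged 65 and over may be just as comorbid.
- **The larger inflation needs a larger shift.** A reader might take 14-22% as the expected size. The RCA is cumulative from 31 May 2023, 2023/2024 doses were given under shared decision-making, and ages 75 and over are recommended universally. The mechanism documented in section 7 reaches roughly a quarter of doses under the assumptions above.
- **Consequences are buffered.** The margin of 2 absorbs a bias of this size when there is no true effect. The protocol says the RCA does not establish association, concedes residual confounding, and sends signals to the SCRI, which removes fixed comorbidity. Nor does the RCA come first for every season: the 2023/2024 SCRI was in Interim report 1 (20 December 2024), ahead of the RCA results in Interim report 3 (08 August 2025).

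These safeguards do not fully replace adjustment. Signal characterisation (section 9.7.3) describes only ABRYSVO recipients with GBS, so it has no comparator against which a comorbidity imbalance would show. The pooled SCRI is powered for 3- to 4-fold risks: Table 1 needs 8,846,154 vaccinees for IRR 2.0 at 21 days and 4,339,623 at 42 days, against about 2 million expected. Near RR = 2, where the bias matters most, it has little power to settle the question.

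**Conclusion.** The point holds in a limited form. Section 9.7.3.1 commits to demographic adjusters and requires no comorbidity measure, although the protocol's own Figure 8 and section 7 give reasons to expect comorbidity to matter. The expected count may therefore be biased, plausibly downward.

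Under the stated assumptions the RR is inflated by about 4-6% if only 2024/2025 recipients aged 65-74 differ, and by 14-22% only if the whole cohort does. If recipients are less comorbid, the error reverses and a real signal becomes harder to detect. The consequence is a distorted reported RR and a higher or lower error rate near RR = 2. It is not a material risk of a signal when the true RR is 1. This is a cheap improvement worth making, not a flaw that invalidates the RCA.

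**What to change.** In section 9.7.3.1, make a comorbidity measure already collected a required adjuster of the expected count at every look, alongside age, gender and race. CCI 0-1 versus 2+ would serve, measured over the same 365-day baseline in both cohorts. Report the demographic-only expected count as a sensitivity analysis, so that the effect of the added adjuster is visible in either direction. Reconcile section 9.7.3.1, which describes adjusting rates, with section 9.9.2, which describes matching.

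Two-level CCI is one reasonable choice. The protocol does not define increased risk for severe RSV disease as CCI 2+, so frailty or specific conditions could be used instead if they capture the selection better.

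The cost is a little programming, since both cohorts come from the same Medicare claims, and sparser strata for a rare outcome. A two-level measure keeps the sparsity small.
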